5 STUDY POPULATION CHARACTERISTICS

5.1 Subject disposition

Subject disposition (date of first and last subject visit, number of subjects included in each analysis set [ES, SS, and FAS]) will be presented overall, by region and for each site by treatment group at completion of AS0008 and overall for the ES.

The number and percentage of subjects in each analysis set (ES, SS and Sub-populations, and FAS) will be presented by treatment group at completion of AS0008 and overall.

The number and percentage of subjects who started, completed and discontinued the study, along with the primary reason for discontinuation will be summarized by treatment group at completion of AS0008 and overall for the SS (a subject will be considered to have completed the study if they attended Visit 21 [Week 208]). For the purposes of the summaries the data will be taken directly from the eCRF page for study termination.

The number and percentage of subjects who started, completed and discontinued study medication, along with the primary reason for medication discontinuation will be summarized by treatment group at completion of AS0008 and overall for the SS (a subject will be considered to have completed study treatment if they received a dose at Visit 20 [Week 204]). For the purposes of the summaries the data will be taken directly from the eCRF page for study medication discontinuation.

For any subjects where the data on the study termination and study medication discontinuation eCRF pages are inconsistent, the data reported on the study termination page will be considered as primary i.e., if a subject is reported as discontinuing from the study, they will be regarded as discontinuing study medication as well (regardless of whether this is reported in the eCRF).

Discontinuations due to AEs will also be summarized by treatment group at completion of AS0008 and overall for the SS.

Subjects who did not meet the eligibility criteria and the inclusion and/or exclusion criteria not met will be listed for the ES.

Subject disposition (subject status, date of informed consent, date of enrollment into AS0009, treatment sequence across AS0008 and AS0009, treatment received at completion of AS0008, start and end date/time and relative days of study medication in AS0009, date of premature study discontinuation and date of final contact) will be listed for the ES. Days relative to the start date of study medication in AS0008 and to the start of study medication in AS0009 will be included for the end date of study medication.

Subject inclusion in each analysis set will be listed for the ES.

Subjects excluded from at least one analysis set, with reason for exclusion, will be listed for the ES. Subjects who were excluded from the SS will have a reason of ‘Subject did not receive at least one dose of study medication during AS0009’, and subjects who were excluded from the FAS will have a reason of ‘Subject did not have a valid measurement of at least one efficacy variable after AS0009 study entry’.

Study and treatment discontinuation reasons and the name of any subsequent treatment will be listed for the ES. Total days on study medication from the start date in AS0008 and from the start date in AS0009 will be included.

These will be calculated as described below:

$$\begin{aligned} & \text{Total days on study medication from start date in AS0009} \\ & = (\text{Date of last dose in AS0009} - \text{Date of first dose in AS0009}) \quad (6) \\ & + 1 \end{aligned}$$

$$\begin{aligned} & \text{Total days on study medication from start date in AS0008} \\ & = (\text{Date of last dose in AS0009} - \text{Date of first dose in AS0008}) \quad (7) \\ & + 1 \end{aligned}$$

For the total days on study medication in AS0008 this will be calculated from the first dose of any medication received regardless of treatment assignment.

Visit dates, including the day relative to the start of study medication in AS0008 and in AS0009, will be listed for the ES.

5.1.1 Impact of COVID-19

A listing of all visits affected by COVID-19 will be presented based on the Enrolled Set including the impacted visit (if applicable), date of visit (if applicable), relationship to COVID-19, impact category and a narrative (short description) of the event. These data will also be summarized by treatment group at completion of AS0008, and overall for the ES for the following:

- Impact of COVID-19 for any reason
- Impact of COVID-19 for any reason by country

In addition, in order to assess the potential impact of COVID-19 on the collection and reporting of efficacy data a separate listing and summary table will be presented to display missing data and data collected via an alternative modality (eg, phone, video call). For the purpose of these displays, missing data will be presented only for visits affected by COVID-19 (as reported on the dedicated eCRF page) ie, missing data at other visits and for other reasons will not be included.

The following efficacy assessments may be collected remotely:

- HADS
- ASQoL
- BASDAI
- BASFI
- SF-36
- PGADA
- TNSP

For visits conducted remotely (as reported on the dedicated eCRF page) it is not possible to assess MASES or BASMI and therefore these assessments will be missing at the specified visit. In addition, for any missed visit or a visit conducted remotely, the CRP assessment will also be missing. Such assessments will be considered as missing due to COVID-19. For these visits it will therefore not be possible to assess ASAS 5/6 response or ASDAS-CRP.

A listing will be presented showing each impacted visit, based on the FAS. This will include the planned visit, the visit date and details of the assessments conducted remotely and/or those missing as a result of COVID-19.

These data will be presented in a summary table by treatment group at completion of AS0008 and overall, for the FAS.

For both the listing and the summary table, only visits at which efficacy assessments are scheduled will be included.

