4.2 Handling of dropouts or missing data

4.2.1 Handling of missing data for efficacy analysis

Calculation of derived efficacy variables in the presence of missing data is described in individual sub-sections of [Section 8.1](#). All derived efficacy variables will be calculated using observed data, and any resulting missing data will be handled as described in this section. All non-responder imputation (NRI) and multiple imputation (MI) as described below will be performed only for subjects in the FAS for AS0009.

For assessments missing during AS0008 which are used in AS0009 for reporting maintenance of response, the imputed value (based on NRI) from the AS0008 database will be used.

For all visits in AS0009 (including AS0009 EV), missing values or values which cannot be constructed due to missing components for binary secondary/other efficacy variables (ASAS40, ASAS20, ASAS5/6) will be imputed using NRI. For each visit, subjects with missing data or who have dropped out of the study will be counted as non-responders. This includes any subjects with missing baseline values.

For missing continuous secondary/other efficacy variables an MI approach will be used. This will be performed for the following variables/endpoints:

- ASAS components:
 - Total Spinal Pain, Question 1 from TNSP
 - Inflammation, derived as the mean of Question 5 and 6 from the BASDAI
- ASDAS-CRP components:

- Total Back Pain, Question 2 from the BASDAI
- Duration of Morning Stiffness, Question 6 from the BASDAI
- PGADA (this is already included below as this is required as a standalone endpoint)
- Peripheral Pain/Swelling, Question 3 from the BASDAI
- CRP

ASDAS-CRP and ASDAS-ID will be determined after MI of the individual components of the ASDAS-CRP (ie, MI will not be applied to the overall ASDAS-CRP score). Note that for CRP the rules for handling measurements that are below the limit of quantification (BLQ) should be followed as per [Section 8.1.2](#). Thus, if any imputed values are <2mg/L these will be replaced with a constant value of 2mg/L for subsequent derivation of ASDAS-CRP. For the ASDAS-ID, the number of subjects within each disease activity category will be derived for each imputation and the mean number of subjects within each category across imputations will be presented.

- BASDAI
- BASFI
- BASMI
- MASES

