8.1.1 Assessment in Axial Spondyloarthritis International Society Response Criteria

The ASAS20 response is defined as an improvement (decrease) of at least 20% and absolute improvement of at least 1 unit on a 0 to 10 numeric rating scale (NRS) in at least 3 of the 4 following domains (Anderson, 2001):

- PGADA
- Pain assessment (total spinal pain, question 1 from total and nocturnal spinal pain questionnaire)
- Function (represented by the BASFI)
- Inflammation (the mean of the BASDAI questions 5 and 6, concerning morning stiffness, intensity and duration)

This must be accompanied by the absence of deterioration in the potential remaining domain. Deterioration is defined as a relative worsening of at least 20% and an absolute worsening of at least 1 unit.

The ASAS criteria for 40% improvement are defined as relative improvement of at least 40% and absolute improvement of at least 2 units on a 0 to 10 NRS in at least 3 of the 4 domains and no worsening at all in the remaining domain (where worsening is defined as any worsening at all relative to baseline).

The comparison of changes to the specified cut-offs (i.e., ≥ 1 or ≥ 2 units) will be based on non-rounded data.

The ASAS 5/6 response is defined as at least 20% improvement in 5 of 6 domains, which includes, in addition to the 4 domains above, spinal mobility (lateral spinal flexion as recorded for BASMI) and CRP as more objective measures (Brandt et al, 2004). In the calculation of the ASAS 5/6 response the actual assessment value for the lateral spinal flexion will be used and not the transformed value used in the calculation of the BASMI score.

If the CRP value is below the lower limit of quantification (LLOQ) defined in AS0008 then it will be set to half of the LLOQ (as described in [Section 8.1.12](#)).

The ASAS partial remission (ASAS-PR) response is defined as a score of ≤ 2 units on a 0 to 10 unit scale in all 4 domains listed above.

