8.1.1.2 Data Handling Rules for ASAS5/6

The ASAS5/6 will be derived based on the data handling rules below. These rules will be implemented prior to performing any NRI procedures and will therefore be integrated as part of any OC summaries.

The rules will apply for all visits in AS0009 where at least one component is present at the specific visit. For summaries of maintenance of response, the ASAS responses at visits in AS0008 will not be re-derived and will be taken directly from the AS0008 database.

- If 5 components are present (and the other component is missing), and all 5 components meet the criteria for improvement, the subject will be considered a responder for ASAS5/6.
- If all components are present and 5 components meet the criteria for improvement, the subject will be considered a responder for ASAS5/6 regardless of whether the remaining component has stayed the same or deteriorated.
- If a single component value is missing at Baseline (and the other 5 components are not missing), the percent and absolute improvement from Baseline for all visits will be treated as 0 for purposes of ASAS response calculations. Thus, the subject may still be considered a responder for ASAS5/6 if the other 5 components all meet the criteria for improvement.
- If more than 1 component value is missing at Baseline, the percent and absolute improvement from Baseline for all visits for those components will be set to 0 for purposes of ASAS response calculations. Thus, the subject would be considered a non-responder for ASAS5/6 at all visits.
- If the Baseline value for a given component is 0 the percent improvement from Baseline is not calculable. In this case the following rules will apply:
 - If the post-Baseline value is also 0, the percent and absolute improvement at that visit will be treated as 0 for purposes of ASAS response calculations.
 - If the post-Baseline value is greater than 0 and the arithmetic change from Baseline is ≥ 1.0 , then that component will be treated as having a 20% worsening and a 1-unit

absolute worsening from Baseline for purposes of ASAS response calculations (i.e., the component has deteriorated). This will not affect the ASAS5/6 response as this is based on improvement only.

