8.5 Impact of COVID-19

Additional sensitivity analyses as a result of the global COVID-19 pandemic are not anticipated as the onset of the pandemic was subsequent to all subjects completing Week 48 and therefore there is no impact on the analysis of the secondary efficacy endpoint.

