12 APPENDICES

12.1 Data Handling Rules for ASAS20, ASAS40 and ASAS5/6 Response

The rules for handling missing data in relation to defining the achievement of ASAS20 and ASAS40 responses are provided in [Table 12-1](#). This table also indicates, where appropriate, the imputation as a non-responder (DTYPE = WC) in the analysis datasets for the NRI analyses. For tables presented on OC data, the data selected will include all instances where DTTYPE is not populated in the analysis datasets.

Table 12-1: Data Handling Rules for ASAS20 and ASAS40

Components	Component Status	ASAS ^a	DTYPE
4 components present	3 or more components improved ≥40% and ≥2 units AND no deterioration in remaining component	Y	
4 components present	3 components improved ≥40% and ≥2 units AND remaining component deteriorated ≥20% and ≥1 unit	N	
At least 1 component present	1 or more component(s) has deteriorated ≥20% and ≥1 unit	N	
3 components present	3 or more components improved ≥40% and ≥2 units	Y	
3 components present	2 components improved ≥40% and ≥2 units AND no deterioration in remaining component(s)	N	WC
3 components present	1 or 0 components improved ≥40% and ≥2 units AND no deterioration in remaining component(s)	N	
2 components present	2 or 1 components improved AND no deterioration in remaining component(s)	N	WC
2 components present	0 components improved	N	
1 or 0 components present	1 or 0 components improved ≥40% and ≥2 units AND no deterioration in remaining component(s)	N	WC

^a Rules are based on ASAS40, similar rules will be implemented for ASAS20 response where improvement is defined as a change ≥20% and ≥1 units.

WC = worst case.

Similar rules for defining the achievement of ASAS5/6 response are presented in [Table 12-2](#).

Table 12-2: Data Handling Rules for ASAS5/6 Response

Components	Component Status	ASAS	DTYPE
6 components present	5 or more components improved $\geq 20\%$	Y	
6 components present	4 or fewer components improved $\geq 20\%$	N	
5 components present	5 components improved $\geq 20\%$	Y	
5 components present	4 components improved $\geq 20\%$	N	WC
5 components present	3 or fewer components improved $\geq 20\%$	N	
4 components present	4 or 3 components improved $\geq 20\%$	N	WC
4 components present	2 or fewer components improved $\geq 20\%$	N	
3 components present	3 or 2 components improved $\geq 20\%$	N	WC
3 components present	1 or 0 component(s) improved $\geq 20\%$	N	
2 components present	2 or 1 components improved $\geq 20\%$	N	WC

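### At COVID-19 remote visits ASAS5/6 normally cannot be met: NRI fails every one, and Table 12-2 leaves only non-responders in the OC summary, so both planned ASAS5/6 estimates after Week 48 are biased down if remote visits are unrelated to response

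*SAP*

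**What the plan says.** **What is lost at a remote visit.** SAP Section 5.1.1 states that at visits conducted remotely "it is not possible to assess MASES or BASMI and therefore these assessments will be missing at the specified visit", and that "for any missed visit or a visit conducted remotely, the CRP assessment will also be missing". It concludes: "For these visits it will therefore not be possible to assess ASAS 5/6 response or ASDAS-CRP".

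**Why that matters for ASAS5/6.** Section 8.1.1 defines the response as at least 20% improvement in five of six domains. Four are patient-reported; the other two are "spinal mobility (lateral spinal flexion as recorded for BASMI) and CRP as more objective measures".

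**How incomplete records are classified.** Under Section 8.1.1.2 a subject with one component missing can still respond: "If 5 components are present (and the other component is missing), and all 5 components meet the criteria for improvement". Section 12.1, Table 12-2, extends the rules to fewer components. With four present and three or four improved, the record is a non-response flagged worst case (WC). With four present and "2 or fewer components improved", it is a non-response with no flag. OC tables take only the unflagged records, and Section 8.1.1.2 says its rules form part of the OC summaries.

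**Which analyses are planned.** Section 4.2.1 sets NRI as the main approach: at each visit, "subjects with missing data or who have dropped out of the study will be counted as non-responders". Table 4-2 and Section 8.3 add OC for ASAS5/6. Response re-derived after multiple imputation (MI) of the components is planned for ASAS40 and ASAS20 only. The ASAS5/6 maintenance-of-response summary, which runs to Week 204, is NRI only (Section 8.3.1).

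**The COVID-19 position.** Section 8.5 says "Additional sensitivity analyses as a result of the global COVID-19 pandemic are not anticipated", on the ground that all subjects had completed Week 48 before the pandemic began.

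**The concern.** ASAS5/6 is also reported at Weeks 96, 156 and 204 (Section 2.2.2.3), so the Week 48 argument in Section 8.5 does not cover it. At those visits a change in how the visit was held, with no change in disease, can turn a responder into a recorded failure.

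The OC summary would normally be the check on NRI. Under Table 12-2 it is not neutral here: remote records that might have been responses leave, and remote records that are certain non-responses stay. Each retained classification is correct, but the selection is one-sided. A decline in ASAS5/6 over the pandemic years could then appear in both planned summaries, and in the maintenance display, and be read as loss of long-term effect. Sections 5.1.1 and 12.1 also give different accounts of the same record: one calls it not assessable, the other assigns it an outcome.

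**Working it through.** The plan gives no response rate, remote share or sample-size calculation for ASAS5/6, so there is no figure to reproduce.

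**Step 1. Classification of a remote visit (four components present, Table 12-2).**

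| Improved, of 4 | Recorded | Flag | NRI | OC |
|---|---|---|---|---|
| 0, 1 or 2 | N | none | failure | kept as non-responder |
| 3 or 4 | N | WC | failure | dropped |

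No row gives Y. The carry-forward rule for BASMI (Section 8.1.5) does not rescue flexion. It applies when one or two of the five measures are missing, whereas all five are missing at a remote visit, and it serves the BASMI score, while ASAS5/6 uses the actual flexion measurement.

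**Step 2. Which visits can be affected.** The final protocol is dated 15 May 2017 (SAP Section 1). Adding 156 weeks gives 11 May 2020, or 4 May with the 7-day window. Section 10.2.4 dates the pandemic from 11 March 2020, so every scheduled Week 156 and Week 204 assessment falls after it. For Week 96, the earliest date is 18 March 2019. If everyone passed Week 48 before 11 March 2020, the latest is about 10 February 2021 (48 weeks on). Week 96 can therefore straddle the start.

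**Step 3. Formulas.** Let p be the true ASAS5/6 rate, r the remote share, and f the share of remote visits with two or fewer of four improved. All three are assumptions. Remote status is taken as unrelated to response.

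- NRI = p(1 − r)
- OC on retained records = p(1 − r) / [(1 − r) + r·f]
- OC on the analysis-set denominator (the general rule in Section 3.1, with a Missing row) = p(1 − r)

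A subject with at most two of four improved can reach at most four of six, so f cannot exceed 1 − p.

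**Step 4. Illustration per 100 subjects, p = 50%, r = 20%, f = 30%.** There are 80 on-site subjects (40 responders, 40 non-responders) and 20 remote (6 with two or fewer improved, 14 with three or four). NRI = 40/100 = 40.0%.

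| OC reading | Responders | Non-responders kept | Missing | % of retained | % of analysis set |
|---|---|---|---|---|---|
| Table 12-2 | 40 | 40 + 6 = 46 | 14 | 40/86 = 46.5% | 40.0% |
| Section 5.1.1 taken literally | 40 | 40 | 20 | 40/80 = 50.0% | 40.0% |

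Only the lower reading with a non-missing denominator returns the assumed truth.

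**Step 5. Range.** With p = 50% and f = 30%:

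- r = 5%: NRI 0.95 × 0.5 = 47.5%; OC 0.475/0.965 = 49.2%
- r = 30%: NRI 0.70 × 0.5 = 35.0%; OC 0.35/0.79 = 44.3%

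At r = 20%, moving f from 20% to 40% moves OC on retained records from 0.40/0.84 = 47.6% to 0.40/0.88 = 45.5%.

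**Step 6. Check by simulation.** One million subjects were simulated with correlated components (latent correlation 0.6; improvement 65% in each patient-reported domain, 50% and 60% in the other two) and 20% remote visits. The true rate was 44.5%, NRI 35.6%, OC under Table 12-2 on retained records 40.4%, and OC with all remote visits removed 44.5%.

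**The case against.** Several objections have force.

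- **Section 5.1.1 may govern.** Taken literally, it makes every remote ASAS5/6 record missing, and OC then does not select on outcome. This stands as an alternative reading, but Table 12-2 is the derivation rule that would be programmed, and nothing exempts remote visits from it. NRI and the maintenance summary stay low under either reading.
- **The 46.5% depends on the denominator.** It does. Under the general rule in Section 3.1, OC would show 40.0%, equal to NRI, with 14% listed as missing. That is no less biased.
- **A remote visit is not always a failure.** A CRP or flexion value from an unscheduled assessment inside the visit window can be mapped to the visit (Section 3.5), and components are combined by assigned visit (Section 8.1). Five components could then exist. This stands.
- **Other information is available.** Section 5.1.1 plans a listing and an FAS table of assessments missing or collected remotely. BASDAI, BASFI, PGADA, spinal pain, BASMI, CRP and ASDAS-CRP are summarised after MI, and ASAS20/40 get component MI. A reader might infer that long-term efficacy as a whole has no reliable estimate. The documents do not support that; the gap is confined to ASAS5/6.
- **NRI is protocol-specified (Section 13.8) and conservative, and ASAS5/6 is only an *other* variable in a descriptive single-arm extension.** True, and this limits the importance. It does not explain why the OC check should lean the same way.

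Fully missed visits, with no components, are flagged WC and leave OC without this selection. The problem is specific to remote visits with patient-reported data.

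**Conclusion.** The point holds for ASAS5/6 at affected Week 96, 156 and 204 visits. Unless a missing component is mapped in, a remote visit cannot be a response. NRI fails all such visits, and OC under Table 12-2 retains only the certain non-responders. Given remote visits unrelated to response, NRI is low by p·r (10 points in the illustration). OC is low by 3.5 points on retained records (50.0 − 46.5), or by the same 10 points on the analysis set. The NRI maintenance summary is low for the same reason. The actual size is unknown because the remote share is not given.

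Two limits apply. If remote visits are related to response, the direction of the OC bias is no longer guaranteed. And a reader might infer that the main efficacy results are compromised: they are not, because the primary variables are safety incidences and the secondary efficacy variables are all at Week 48, before the pandemic. This is a worthwhile repair to one secondary-tier display, not a threat to the study's conclusions.

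**What to change.** 1. **Reconcile Section 5.1.1 with Table 12-2.** State that any ASAS5/6 record with fewer than five components is missing in the OC summary, whatever the number improved, and that the OC percentage uses non-missing records as its denominator. The rows for five components can stay, since both outcomes can be retained there. Cost: a text and programming change, and some certain non-responses are discarded.

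2. **Add one sensitivity table** with ASAS5/6 re-derived after MI of all six components, as already planned for ASAS20/40. Five components (PGADA, BASFI, total spinal pain, inflammation, CRP) are already imputed under Section 4.2.1; only raw lateral spinal flexion is new. For this purpose impute CRP on the log scale. As written, logs are taken after imputation and imputed values below 0.16 mg/L are replaced with 0.08 mg/L, so low normal-model draws could register as false CRP improvement. Cost: one more imputed variable, one extra table, and reliance on missing at random.

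3. **Amend Section 8.5** to say that its reasoning covers Week 48 only, and point to the new table for later ASAS5/6 visits and for interpreting the maintenance summary.
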